Primary Endpoints	
 1. Capture of the Left and/or Right Phrenic Nerve > 80% with an output parameter of < 10.5 volts. 2. WOB (Work of Breathing) kept between 0.2 joules/L and 2 joules/L for 80% of stimulated breaths.
Secondary Endpoints	
 1. The percentage of patients who receive safe and successful placement of the multipolar lead in the left and right phrenic nerve utilizing ultrasound guidance will be determined. 2. Phrenic nerve stimulation in synchrony with Mechanical Ventilation (MV) breaths will be measured to verify that it occurs with inspiration. 3. The percentage of patients who experience one or more serious device/procedure-related adverse events during the study will be reported.
Additional Study Data	
 1. Time to weaning from mechanical ventilation data will be collected. 2. Diaphragm thickness at 0, 24 and 48 hours.

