6.10 Primary Performance Endpoint: Stimulation Pulse to Capture the Diaphragm

The ability of the stimulation pulse to capture the diaphragm will be assessed using WOB (Work of Breathing Measurements). A logistic regression model with successful capture as the outcome will be used. The model will include repeated measurements within a subject.

6.10.1 Model:

capture = (timepoint) (subject)

where subject is a random effect, and the outcome of capture is yes/no based on whether the stimulation captures the diaphragm.

6.10.2 Hypothesis:

H_0 : The proportion of capture is less than or equal to the performance goal (PG) of 90%.

H_0 : $\hat{p}_1 \leq PG$

H_A : The proportion of capture is greater than the performance goal of 90%.

H_A : $\hat{p}_1 > PG$,

where \hat{p}_1 is the estimated proportion of capture from the logistic model accounting for repeated measurements within a subject.

6.10.3 Sample Size:

The following assumptions were the basis for the sample size calculation for the performance endpoint evaluating stimulation capture of the diaphragm:

- Power: 80%
- 1-sided α : 0.025
- Performance goal: 90%
- Expected success rate: 97.5%

With an anticipated success rate of 97.5% and a performance goal of 90%, 80 observations would yield $\geq 80\%$ power. Note that, for the purposes of sample size calculations, the observations are assumed to be independent. However, the primary analyses will account for within patient correlation, as described below. Increasing the number of observations will increase the statistical power.

6.10.4 Methods:

The proportion of successful capture will be analyzed using a logistic regression model accounting for patient as a random effect. The null hypothesis will be tested comparing the lower bound of the 95% two-sided confidence interval for the estimated percent agreement to the performance goal of 90%. If the lower bound is greater than 90%, the null hypothesis will be rejected and the endpoint will be considered met.

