6.13 Electrocardiogram (ECG) and X-ray

The electrocardiogram testing will be conducted using 12 leads prior to the stimulation and during the stimulation approximately every 24 hours following standard hospital procedures for running this test so that a cardiologist can determine if there have been any ECG changes during or post stimulation.

A routine chest x-ray will be taken prior to the stimulation and at or before the 30 day follow up, to determine if there has been any obvious change in lung volume or degree of atelectasis (in comparison to the contralateral lung as a consequence of stimulation).

6.14 Secondary Performance Endpoint: Analyzing Phrenic Nerve Stimulation in Synchrony with MV Breaths

A breath by breath stim count analysis will be performed to determine the effectiveness of electrical stimulation on the inspiratory breaths stimulated. Effectiveness will be determined by measuring an effect on the work performed by the diaphragm and its ability to remain within normal physiological levels of work of breathing.

Figure 3. Sample Data Acquisition Data using Labchart for Qwye, Pwye, WOB and Stim Signals

The analysis will be performed for WOB as follows. A count will be performed to determine the number of stimulated breaths the measured WOB falls within a predetermined upper and lower control level for the stimulated breaths. This will be compared to the number of breaths electrically stimulated. These counts will be used to determine the effectiveness of electrical stimulation based upon percentage of electrical stimulation signals capturing breaths as intended.

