In addition, there may be additional analyses conducted and other tables and graphs created for the final clinical study report based on the outcomes of the initial analyses and additional data points of interest.

An interim analysis may be run and this was allowed in the protocol. See Statistical Methodology section for greater details.

PRIMARY ENDPOINTS

The primary endpoints for the study relate to the ability of the therapy to mobilize the diaphragm and of the PEPNS system to stimulate specific levels of work of breathing.

- Capture of the Left and/or Right Phrenic Nerve > 80% with an output parameter of < 10.5 volts.
- WOB (Work of Breathing) kept between 0.2 Joules/L and 2 Joules/L for 80% of stimulated breaths.

The capture of the left and right phrenic nerve will be demonstrated during setup and by maintaining the WOB between 0.2 and 2 Joules/L. The stimulation voltage resultant from the tissue impedance and the user set current will be logged and evaluated to ensure it is less than 10.5 volts. Capture will also be evaluated in terms of synchrony.

The ability of the stimulation pulse to capture the diaphragm will be assessed using WOB (Work of Breathing Measurements). A logistic regression model with successful capture as the outcome will be used. The model will include repeated measurements within a subject.

Model:

$\text{capture} = (\text{timepoint}) (\text{subject})$

where subject is a random effect, and the outcome of capture is yes/no based on whether the stimulation captures the diaphragm.

Capture for this analysis is defined as synchrony of the stimulated breath with the output parameter < 10.5 volts and WOB between 0.2 and 2.0 Joules/L. Synchrony will be achieved if the lag time between start of inspiration and start of stimulation is less than 88 ms.

Hypothesis:

H_0 : The proportion of capture is less than or equal to the performance goal (PG) of 80%. Note: This hypothesis used a 90% performance goal in the protocol for the purposes of sample size calculation to ensure that there would be sufficient data to achieve the 80% performance goal when taking into account lost to follow up due to death, etc.

$H_0: \hat{p}_1 \leq \text{PG}$

H_A : The proportion of capture is greater than the performance goal of 80%.

$H_A: \hat{p}_1 > \text{PG}$,

where \hat{p}_1 is the estimated proportion of capture from the logistic model accounting for repeated measurements within a subject.

Sample Size:

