This sample size calculation reflects the use of a 90% performance goal as noted above in the hypothesis section and in the CIP. Again, this was done to ensure that there would be sufficient data to achieve the 80% performance goal when taking into account lost to follow up due to death, etc. The following

	PEPNS Study Statistical Analysis Plan <small>CONFIDENTIAL: THIS DOCUMENT AND ALL INFORMATION CONTAINED HEREIN IS PROPRIETARY TO STIMDIA MEDICAL, INC. AND IS NOT TO BE DISCLOSED WITHOUT THE EXPRESS WRITTEN PERMISSION OF STIMDIA MEDICAL, INC.</small>	Document Number SAP0001	Rev. Level 1
---	--	-----------------------------------	------------------------

assumptions were the basis for the sample size calculation for the performance endpoint evaluating stimulation capture of the diaphragm:

- Power: 80%
- 1-sided α : 0.025
- Performance goal: 90%
- Expected success rate: 97.5%

With an anticipated success rate of 97.5% and a performance goal of 90%, 80 observations would yield $\geq 80\%$ power. Note that, for the purposes of sample size calculations, the observations are assumed to be independent. However, the primary analyses will account for within patient correlation, as described below. Increasing the number of observations will increase the statistical power.

Methods:

The proportion of successful capture will be analyzed using a logistic regression model accounting for patient as a random effect. The null hypothesis will be tested comparing the lower bound of the 95% two-sided confidence interval for the estimated percent agreement to the performance goal of 80% (see note above). If the lower bound is greater than 80%, the null hypothesis will be rejected and the endpoint will be considered met.

If the logistic regression model does not converge (i.e. it does not provide reliable estimates of diaphragm capture), other methods will be used to characterize the capture rate. The method used will be dependent on the data and will be described in detail along with the reasons for using that method.

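### The protocol's success rule tests capture against 90%, the SAP tests it against 80%, and the SAP's sample-size explanation does not account for the difference

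*SAP*

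**What the plan says.** **Protocol.** The Study Summary and section 5.1 list the first primary endpoint as "Capture of the Left and/or Right Phrenic Nerve > 80% with an output parameter of < 10.5 volts". No hypothesis, confidence bound or test is attached there. The protocol's only inferential rule for capture is in section 6.10:

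- 6.10.2 gives the null hypothesis as "The proportion of capture is less than or equal to the performance goal (PG) of 90" per cent.
- 6.10.3 sizes the study on a 90% goal, an expected rate of 97.5%, one-sided alpha 0.025 and 80 observations treated as independent, for at least 80% power.
- 6.10.4 gives the decision rule: "If the lower bound is greater than 90%, the null hypothesis will be rejected and the endpoint will be considered met".

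**SAP.** Section 2 (Hypothesis and Methods) and section 6 replace 90% by 80%, at the interim as well as the final analysis. The note under the hypothesis says "This hypothesis used a 90% performance goal in the protocol for the purposes of sample size calculation". The Sample Size paragraph adds that "this was done to ensure that there would be sufficient data to achieve the 80% performance goal" after losses such as deaths. It then repeats the protocol's power statement for the 90% goal. Section 9, where deviations would be justified, is marked as not applicable.

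**Capture variable.** Protocol 6.10 says "The ability of the stimulation pulse to capture the diaphragm will be assessed using WOB (Work of Breathing Measurements" and gives a yes/no outcome without further criteria. SAP section 2 says "Capture for this analysis is defined as synchrony of the stimulated breath with the output parameter < 10.5 volts" and also requires work of breathing (WOB) within 0.2 to 2.0 J/L. Section 11 codes the three conditions jointly, with a lag limit of 88 ms.

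**The concern.** The two documents set two success thresholds for one primary endpoint. The SAP's reason fits only one of the three uses of 90% in the protocol. A null value defines the claim being tested, so lowering it changes the claim. An allowance for loss changes the number of observations and leaves the null alone. Section 6.10 says nothing about loss to follow-up.

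A reader of the SAP alone would learn that the protocol's hypothesis used 90%, but not that the protocol's test could fail on the result the SAP reports as met. The threshold also affects conduct: if the interim analysis is run, it decides whether enrolment continues.

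The rate being compared may differ too. If protocol capture means the WOB criterion alone, the SAP composite can never exceed it, and the two verdicts would then refer to different quantities.

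**Working it through.** **Inputs (protocol 6.10.3, repeated in SAP section 2).** n = 80 independent observations, expected rate p1 = 0.975, one-sided alpha 0.025. The goal is p0 = 0.90 in the protocol and 0.80 in the SAP. The calculations use one capture definition throughout.

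**1. The plan's own power figure (goal 90%).** The documents do not name the test.
- Arcsine: Φ(2(asin√0.975 − asin√0.90)√80 − 1.96) = 83.0%.
- Mid-P (reject at 77 of 80 or more): 85.9%.
- Score with null variance: Φ((0.075√80 − 1.96 × 0.30)/√(0.975 × 0.025)) = Φ(0.53) = 70.2%.
- Exact binomial (reject at 78 or more): 67.7%.

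The stated power of at least 80% is reproduced by some standard methods and not by others, so it is not shown to be wrong.

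**2. Where the two rules part.** The critical value is the smallest x with P(X ≥ x | n = 80, p0) ≤ 0.025.
- p0 = 0.80: x = 72 (size 0.0131), Clopper-Pearson lower bound 81.2%.
- p0 = 0.90: x = 78 (size 0.0107), lower bound 91.3%.

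Results of 72 to 77 out of 80 (lower bounds 81.2% to 89.4%) are met under the SAP and not met under protocol 6.10.

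**3. How often that happens.**

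| True capture | Met, SAP: P(X ≥ 72) | Met, protocol: P(X ≥ 78) | Split: P(72 ≤ X ≤ 77) |
|---|---|---|---|
| 90% | 59.3% | 1.1% | 58.2% |
| 95% | 98.2% | 23.1% | 75.1% |
| 97.5% | 99.98% | 67.7% | 32.3% |

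The split depends on the method: at a true 97.5%, mid-P (critical values 71 and 77) gives 14%.

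**4. The goal as a loss allowance.** For the 80% goal at a true 97.5%, 25 observations give 53.1% exact power and 26 (critical value 25) give 86.3%. Read as an allowance over 26, the 80 observations would imply a loss of 1 − 26/80 = 67.5%. Neither document states a loss rate or says that n was inflated from a smaller number.

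**5. Clustering.** SAP section 11 codes every stimulated breath, so observations are correlated within patient. Assume 10 equal patients with m breaths each. The effective n is 10m/(1 + (m − 1)ICC), which tends to 10/ICC as m grows. The ICCs below are assumptions. The exact binomial at the effective n only approximates the random-effects model.

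| Assumed ICC | Effective n | Critical values (80%, 90%) | Met at true 90%: SAP, protocol | Split at true 97.5% |
|---|---|---|---|---|
| 0.05 | 200 | 172, 189 | 97.3%, 1.7% | 0.5% |
| 0.10 | 100 | 89, 96 | 70.3%, 2.4% | 10.6% |
| 0.20 | 50 | 46, 50 | 43.1%, 0.5% | 71.0% |

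The 71.0% partly reflects discreteness, because the exact 90% rule then needs 50 of 50. Mid-P (critical value 49) gives 34.8%.

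**6. Interim analysis.** SAP section 6 changes the intervals to 98.75% and 98.06% but still compares the bound with 80%, so the disagreement between 80% and 90% remains.

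**The case against.** The strongest reply is that 80% is no newly invented, easier goal. It is the protocol's listed primary endpoint, stated twice, so the conflict begins inside the protocol and the SAP sides with the list. The SAP also discloses the 90%: its note sits under the null hypothesis, and its decision rule refers back to the note. The goal and capture definition in the SAP are clear. The composite is stricter than WOB alone, and the listed endpoint already carries the voltage limit, so the SAP is not more lenient in every respect. This is a small first-in-human study whose main methods are described as descriptive. The split probabilities vary widely with the method and the assumed ICC.

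Much of this stands. The change is not hidden, 80% may be the intended goal, and the probabilities are illustrations. The difference in capture definition is conditional on how 6.10 is read; the WOB count described in protocol 6.14 belongs to a secondary endpoint and does not settle it.

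The reply does not remove the conflict. The endpoint list contains no test, so 90% is the only inferential rule in the protocol. The note does not say that 90% was the threshold for success, and its reason does not appear in 6.10. Despite the descriptive framing, the study has a formal hypothesis, an alpha level and a met/not-met verdict.

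**Conclusion.** The concern holds. Protocol 6.10 and the SAP give opposite verdicts whenever the lower bound for the same capture variable falls between 80% and 90%, and the SAP's note does not explain the change of success rule. This follows from the text and needs no modelling.

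The practical size is uncertain. With 80 independent observations and exact limits, the chance of a split verdict is 58% at a true 90%, 75% at 95% and 32% at 97.5%. With 10 patients and many correlated breaths, it runs from 0.5% to 71% at a true 97.5% over assumed ICCs of 0.05 to 0.20. The effect of the composite definition was not modelled.

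The sample size is ample for the 80% goal if observations are independent (99.98% exact power at a true 97.5%), but the SAP does not state this.

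On timing, SAP sections 7 and 8 describe a cohort of ten in the past tense. The text available does not show when 80% was fixed or whether capture data had been seen, and no inference is drawn. The matter should be fixed; it does not show that 80% is the wrong goal.

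**What to change.** 1. Correct the SAP's notes under Hypothesis and Sample Size to say that 90% was the protocol's null value and success threshold as well as its sizing input.
2. Record the 80% rule as a change from protocol 6.10 that reconciles it with the endpoint list. Give the reason, and state when it was fixed relative to access to capture data.
3. Report the lower bound, at the confidence level that applies, against both 80% and 90%, and say which rule each comparison serves.
4. State with each verdict whether capture means WOB alone or the composite of lag, WOB and voltage.
5. State power for the 80% goal and name the method.

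The cost is wording in the SAP and report, and one bound compared with two values; no extra data are needed. The sponsor may have to report that the protocol's 90% hypothesis was not rejected.

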12. DATA RECORDING AND SUBMISSION REQUIREMENTS

Data

All aspects of the study will maintain patient privacy and be Declaration of Helsinki and General Data Protection Regulation (GDPR) and Data Protection Act 2018 compliant.

All **raw data** will be entered into an Excel or validated spreadsheet format (with patient names excluded) and include all data collected on the patients up to the time the data is frozen including baseline, procedure, and all follow up data available. All data sets provided shall be clean with all queries resolved.

The following are the types of data in the study:

RAW DATA:

1. PEPNS System electronic archive – data recording by the PEPNS system will be electronically archived by Stimdia Medical.
2. Patient history file – this document will confirm patient meets inclusion and exclusion criteria while also documenting all demographic and physiology aspects of the enrolled patient.
3. PEPNS System procedure report – documentation of procedure related information, e.g., sedation, ventilation, stimulation, ultrasound, test article documentation, procedure step checklist and procedure related specifics noted.

CASE REPORT FORMS (CRF):

1. Screening form
2. Index procedure form
3. Adverse event form
4. Patient disposition form
5. Protocol deviation form
6. Device malfunction form
7. Follow up form

SPREADSHEET AND ANALYSES:

1. All data relevant to analysis will be maintained in a validated Excel spreadsheet until the completion of the study. The master spreadsheet will be validated and maintained by Stimdia Medical. All Excel files used for the data analysis must be password protected and only authorized study personnel can have access to the passwords.

Interim analysis and results will be reviewed with the steering committee in a periodic manner.

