An interim analysis of the primary endpoints may be done on the first 10 patients that were stimulated on both phrenic nerves. If they are met the secondary and other remaining analyses will also be performed. If not, the study will continue to enroll patients and all study endpoints and additional analyses will be analyzed when enrollment has been completed. If an interim analysis is done, the significance level used for testing will be 0.0125. At the final analysis (if needed) the significance level used for testing will be 0.0194. These levels were derived using a power cumulative error spending function with the parameter (rho) set to 1.0. This setting produces Pocock type boundaries (i.e. approximately equal spending for the two tests).

If an interim analysis is not done, the final analysis will use a significance level of 0.025 for testing the primary endpoints.

SECONDARY ENDPOINTS

The secondary endpoints are safety related and examine the percentage of patients who receive safe and successful placement of the multipolar lead in the left and right phrenic nerve utilizing ultrasound guidance and the percentage of patients who experience one or more serious device/procedure-related adverse events during the study.

- The percentage of patients who receive safe and successful placement of the multipolar lead in the left and right phrenic nerve utilizing ultrasound guidance will be determined.
- Phrenic nerve stimulation in synchrony with Mechanical Ventilation (MV) breaths will be measured to verify that it occurs with inspiration.
- The percentage of patients who experience one or more serious device/procedure-related adverse events during the study will be reported.

	PEPNS Study Statistical Analysis Plan	Document Number SAP0001	Rev. Level 1
<small>CONFIDENTIAL: THIS DOCUMENT AND ALL INFORMATION CONTAINED HEREIN IS PROPRIETARY TO STIMDIA MEDICAL, INC. AND IS NOT TO BE DISCLOSED WITHOUT THE EXPRESS WRITTEN PERMISSION OF STIMDIA MEDICAL, INC.</small>			

Safe and Successful Lead Placement

The percentage of patients who received safe and successful placement of the multipolar lead on the Left and right phrenic nerve utilizing ultrasound guidance will be evaluated in terms of the mean and standard deviation for preparation, placement, securement, removal and twitching. Twitching includes neck spasms, arm movement, shoulder movement on unwanted visible stimulation. This will be reviewed on a site basis, by neck circumference and BMI.

Adverse Events

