If an interim analysis is performed, the database will be temporarily locked at the time of the interim analysis and the clinical study report will include the date that the data was transferred from the database to the statistician for the interim analysis. It will also specify whether or not the data had been monitored. The secondary end points and other remaining interim analyses will only be performed if the primary endpoints were met. If not, the study will continue to enroll patients and all study endpoints and additional analyses will be analyzed when enrollment has been completed. At the interim analysis the significance level used for testing will be 0.0125 which translates into calculating a 98.75% two-sided confidence interval on the capture rate and comparing the lower bound to 80%. At the final analysis (if needed) the significance level used for testing will be 0.0194 which translates into calculating a 98.06% two-sided confidence interval on the capture rate and comparing the lower bound to 80%. These levels were derived using a power cumulative error spending function with the parameter (rho) set to 1.0. This setting produces Pocock type boundaries (i.e. approximately equal spending for the two tests).

	PEPNS Study Statistical Analysis Plan <small>CONFIDENTIAL: THIS DOCUMENT AND ALL INFORMATION CONTAINED HEREIN IS PROPRIETARY TO STIMDIA MEDICAL, INC. AND IS NOT TO BE DISCLOSED WITHOUT THE EXPRESS WRITTEN PERMISSION OF STIMDIA MEDICAL, INC.</small>	Document Number SAP0001	Rev. Level 1
---	--	-----------------------------------	------------------------

7. MEASURES TO ADJUST FOR MULTIPLICITY, CONFOUNDERS, HETEROGENEITY, ETC.

Since the study cohort was 9 Caucasian men and 1 Caucasian woman and study was very small no heterogeneity, multiplicity or confounder statistical analyses will be run. However, summary data may be presented for the different types of patients (neuro trauma, COPD etc.) to try and see if there were any trends or if therapy was more effective for one of the patient populations since this was one of the study objectives.

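### The interim look is optional and the full one-sided 0.025 returns if it is not done; with no rule that the choice precedes sight of capture data, the error rate could exceed 0.025.

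*SAP*

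**What the plan says.** SAP section 2 (Primary Endpoints) sets the overall level as "1-sided α : 0.025" and then makes the interim a possibility: "An interim analysis of the primary endpoints may be done on the first 10 patients" with stimulation on both sides. Two routes follow.

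- With a look: "If an interim analysis is done, the significance level used for testing will be 0.0125", and "At the final analysis (if needed) the significance level used for testing will be 0.0194".
- Without a look: "If an interim analysis is not done, the final analysis will use a significance level of 0.025 for testing the primary endpoints".

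SAP section 6 repeats that the look is conditional. It turns 0.0125 and 0.0194 into two-sided intervals of 98.75% and 98.06%, whose lower bounds are compared with 80%. Without an interim, the interval is the ordinary two-sided 95%. If the primary endpoints are not met at the interim, enrolment continues; there is no futility stop. For an interim that is performed, section 6 asks for a temporary database lock, a reported data-transfer date and a statement on whether the data had been monitored.

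The protocol's Study Summary describes an open-label, non-randomized study. Protocol section 12 has the sponsor archive the system recordings and keep the master spreadsheet, and adds: "Interim analysis and results will be reviewed with the steering committee in a periodic manner". Protocol section 6 caps enrolment at 20 and lets the final number depend on study duration and enrolment rate.

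**The concern.** The two routes end at different final levels, and nothing fixes which route is taken before capture data are available. The safeguards in SAP section 6 apply only to an interim that is acknowledged as performed. An informal view of the first ten bilateral patients that is never called an interim leaves no required record.

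The reward for not calling it one is material. After a declared look, the final test uses a 98.06% interval, a one-sided level of 0.0097. Without one it uses a 95% interval, a one-sided level of 0.025, which is about 2.6 times as large (0.025 / 0.0097).

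What is at stake is whether the claim that the capture endpoint was met carries the one-sided 0.025 error rate that the SAP states.

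**Working it through.** **Inputs**

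- Overall level: one-sided 0.025 (SAP section 2).
- Interim: 0.0125, applied as a 98.75% two-sided interval, so one-sided (1 − 0.9875)/2 = 0.00625 (SAP section 6).
- Final after an interim: 0.0194, applied as a 98.06% two-sided interval, so one-sided (1 − 0.9806)/2 = 0.0097.
- Final without an interim: one-sided 0.025.
- Information fraction t, taken as the share of bilateral patients. Enrolment is at most 20 (Protocol section 6), and the first two are left-only and count for safety only (SAP section 2), leaving at most 18. So t is at least 10/18 = 0.556. The value t = 0.5 is implied by 0.0125/0.025 but would need 20 bilateral patients.

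**Model.** At a true capture rate equal to the goal, the interim and final statistics Z1 and Z2 are treated as standard normal with correlation √t.

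**Step 1: the SAP's own levels.** Power spending with rho = 1 gives cumulative alpha 0.025 × t. At t = 0.5 this is 0.025 × 0.5 = 0.0125, as stated. The matching final level, with efficacy testing only, solves

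0.0125 + P(Z1 ≤ 2.241, Z2 > c) = 0.025,

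which gives 0.0168 one-sided, not 0.0194. The value 0.0194 comes out (0.01942) if a binding futility bound with rho = 1, beta 0.20 and t = 0.5 is added. The SAP contains no such stop.

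**Step 2: worst case of the open choice.** The look is declared only if it passes; otherwise it is called not done and the final test uses 0.025:

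error = P(Z1 > c1 or Z2 > 1.960) = a1 + 0.025 − P(Z1 > c1 and Z2 > 1.960).

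At t = 10/18:

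- 98.75% interval (a1 = 0.00625, c1 = 2.498): 0.00625 + 0.025 − 0.0036 = 0.0276.
- 0.0125 read as one-sided (c1 = 2.241): 0.0125 + 0.025 − 0.0060 = 0.0315.

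| Bilateral patients at the end | t | Interim by 98.75% interval | Interim at one-sided 0.0125 |
|---|---|---|---|
| 20 (above the maximum of 18) | 0.500 | 0.0280 | 0.0322 |
| 18 | 0.556 | 0.0276 | 0.0315 |
| 16 | 0.625 | 0.0271 | 0.0307 |
| 14 | 0.714 | 0.0265 | 0.0295 |

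**Step 3: choice made without the data.** If the decision is independent of the capture results, the route without a look is a single test at one-sided 0.025, and its error is 0.025.

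**Step 4: would making the look mandatory be enough?** Not with the present levels. At t = 10/18:

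- 0.0125 and 0.0194 as one-sided levels: 0.0267.
- 98.75% and 98.06% intervals as written: 0.0137.
- One-sided 0.0125, then 0.0174: 0.0250.

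At t = 0.5 the pair 0.0125 and 0.0168 gives 0.0250.

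**The case against.** The best defence is that the SAP's rule, followed honestly, does not give full alpha back after a failed formal look: once the interim test has been done, the final level is 0.0194. A performed interim is also traceable through the lock and the transfer date. Inflation therefore needs a look that is taken, or informally seen, and later not acknowledged. That is right, and it is why the point is conditional. The safeguards still do not cover an informal look, and no sentence requires the decision to be made first.

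It can also be said that this is a small first-in-human study whose SAP calls its main methods descriptive, and that the excess is small. The size is indeed modest. But the same SAP sets a hypothesis, a performance goal, a one-sided alpha and a spending function, and calls the endpoint met on that test.

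A reader might go further in three ways that the documents do not support.

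- That capture results were already known when the SAP was written. Section 7 says "Since the study cohort was 9 Caucasian men and 1 Caucasian woman", and Table 3 lists ten patients, P03 to P12. This shows that the cohort had been identified. The result cells of Table 3 are blank, and the periodic review in Protocol section 12 does not mention capture data.
- That error control always requires the look to be fixed in advance. A choice made independently of the data also preserves the level, and fixing the look while keeping 0.0194 as a one-sided level would not.
- That the ten-patient analysis could be relabelled as final, with 0.025 used at both points. This would give 0.0406 at t = 10/18, but no such plan is stated.

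**Conclusion.** The gap is real and conditional. The SAP allows the final level to depend on a choice that nothing separates from the data, so the one-sided error rate could reach about 0.0276 with the intervals as specified, an excess of about 0.0026 over 0.025. If 0.0125 is meant as one-sided, it could reach 0.0315, an excess of about 0.0065. These are worst cases at 10 of 18 bilateral patients and shrink if fewer are enrolled. It would be wrong to conclude that the error rate does exceed 0.025, or that the sponsor has chosen or will choose by the data.

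The figures assume asymptotic normality, t equal to the share of bilateral patients, and a single test of the combined capture indicator. With 10 to 18 patients and a random-effect logistic model, the actual error may differ. The point is worth acting on because the repair needs only wording.

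**What to change.** In SAP sections 2 and 6:

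1. State that the interim on the first 10 bilateral patients will be done.
2. Delete the sentence that restores 0.025, so that the group-sequential final level applies whenever enrolment continues past that point.
3. State that the other periodic steering-committee reviews cover safety and conduct only, with a matching sentence in Protocol section 12.
4. Give both levels on the one-sided scale, with the final level recomputed without a futility stop. For a one-sided 0.0125 interim it is about 0.0174 at t = 10/18, or 0.0168 if t = 0.5 is kept as the design value, in place of 0.0194.
5. Make the intervals match: 97.5% two-sided at the interim (1 − 2 × 0.0125), and 96.52% at the end for 0.0174 (1 − 2 × 0.0174) or 96.64% for 0.0168.

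The cost is SAP and protocol wording, plus a final level somewhat stricter than 0.025 (0.0174 or 0.0168) if the study continues beyond 10 patients. Against the 98.06% interval now written for the final test after an interim, the recomputed level is less strict.
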